## 1.0 Introduction

For most patients with locoregionally advanced head and neck cancer, chemoradiotherapy can improve local control and survival, and can achieve organ preservation. This was first demonstrated in the Veterans Affairs Cooperative Study Group prospective randomized landmark trial comparing an organ preservation approach (induction chemotherapy followed by definitive radiation, based on chemotherapy response) to the standard treatment of laryngectomy with radiation. Sixty six percent of the surviving patients had successful larynx preservation with no decrease in survival. Subsequent trials at multiple other institutions have confirmed these results.

Unfortunately, this improved tumor outcome resulting from the administration of concurrent chemoradiotherapy does not extend to older patients and those with coexisting medical conditions and poor performance status. In the RTOG 91-11 Intergroup Study, the rate of high-grade toxic effects was greater with the chemotherapy-based regimens (81% vs. 61% with radiotherapy alone). The rate of grade 3 and 4 acute mucositis was 20% and 24% in the chemotherapy followed with radiotherapy and the radiotherapy alone arms, respectively, and was doubled in the concurrent chemoradiotherapy arm (43%  $p < 0.05$ ). Also, more deaths that may have been related to therapy were reported in the concurrent chemoradiotherapy arm (5%, compared with 3% in each of the other arms). Enhanced toxicity, primarily mucositis and late dysphagia, were also reported in other studies of concurrent chemoradiotherapy. Mucositis and dysphagia are the main barriers to winning the battle against head and neck cancer.

Therefore, it is not surprising that age has a dramatic impact on the benefit of concurrent chemotherapy with radiation. A meta-analysis of over 15,000 patients, evaluating the impact of age on patients treated with either concurrent chemoradiotherapy or altered fractionation revealed no benefit to older patients (age>70years). This lack of benefit is due, in part, to increased morbidity and mortality of treatment. This study addresses the need to develop less toxic therapies for patients who are older and/or have co-morbidities.

EGFR^1 plays a key role in head and neck cancer, in that its over-expression is associated with more aggressive behavior, and its blockade increases the survival of patients treated with radiation without increasing toxicity. We hope to determine the pharmacodynamic profile of response in patients receiving cetuximab and radiation, so that we can determine who benefits from this extremely expensive and moderately toxic therapy.

### 1.1 Study Hypothesis and Rationale

Bonner *et al* investigated the benefit of the addition of cetuximab to radiation. It was concluded that cetuximab improves locoregional control and reduces mortality without increasing the common toxic effects associated with radiotherapy to the head and neck. In our study, we propose to select locally advanced head and neck cancer patients, who are older than age 70 or are not deemed candidates for chemotherapy. This group was not extensively investigated in the earlier randomized trial, in that

---

 Abbreviations: **CR**, complete response; **EGFR**, epidermal growth factor receptor; **MAPK**, mitogen-activated protein kinase; **PI3K**, phosphatidylinositol 3-kinase; **PR**, partial response; **RT**, radiation treatment/therapy; **STAT**, signal transducer and activator of transcription; **TMA**, tissue microarray.

90% of patients in the Bonner study had a KPS of 80 or greater, and the median age of the patients was 57. The primary end-point of this trial is to characterize local progression free survival in these patients, when treated with cetuximab+radiation.

We also propose to develop a molecular pharmacodynamic predictor of local control after treatment with combination cetuximab-radiation. We hypothesize that tumor EGFR degradation and other markers of down-stream EGFR inhibition as well as novel phosphoproteomic markers observed in tumor biopsies taken 7 days after the administration of cetuximab, will predict the effectiveness of cetuximab-radiation. The first biopsy will be obtained prior to administration of the loading dose of cetuximab. Prior to initiation of cetuximab concurrent with radiation, on Day 7, following the cetuximab loading dose, a tumor biopsy for the biomarkers will be obtained. We hypothesize that tumors that do not demonstrate the changes that correlate with response after cetuximab in the *in vivo* preclinical studies are more likely to progress following cetuximab-radiation therapy compared to those that show changes that correlate with response. If our hypothesis is validated, we will gain a tool that will help identify patients who are most likely to benefit from radiation and cetuximab, a very expensive and moderately toxic treatment.

In the Bonner trial and in the Vermorken study there was an increased survival benefit that was associated with oropharynx sites. High risk HPV (human papilloma virus) infection has been implicated both as an etiologic factor and as a prognostic factor for survival and response to therapy. HPV is also typically associated with a younger cohort of patients, however as the high risk HPV infected cohort ages, we do expect to see more patients in their 70s and beyond who will have HPV-related head and neck cancers. Thus, we postulate the EGFR inhibition will work better in HPV positive tumors. We will investigate the presence of HPV in the tumor tissue biopsies by a variety of assays. We will also examine the p53 status using RNA isolated from the tumor biopsy since HPV positive tumors most frequently have wild type p53 which may also contribute to the high response rate of these tumors.

## 1.2 EGFR inhibitors in head and neck cancer

Initial *in vitro* studies demonstrated that prolonged exposure of cells to EGF could enhance the effects of radiation in head and neck cancer cells. It is likely that this radiosensitivity was achieved through EGF-induced EGFR degradation. Additional studies showed that monoclonal antibodies that target EGFR could increase radiation-induced apoptosis. Furthermore, there was an inverse correlation between EGFR expression levels and radiation response. This relationship between EGFR expression and poor prognosis was confirmed in human head and neck carcinoma samples. A variety of preclinical studies have demonstrated that EGFR inhibitors can increase radiation sensitivity in both *in vitro* and *in vivo* model systems. While the majority of studies have reported additive effects resulting from the combination of EGFR antagonists and radiotherapy *in vitro*, the same combination produces synergistic effects in xenograft models. This may be secondary to EGFR inhibitors and radiation impact on several downstream signaling pathways. These include pathways regulating cellular proliferation and apoptosis, which would

be evident in both in vitro and in vivo, and pathways regulating angiogenesis and tumor invasion, which might be detectable only in tumor xenograft models.

While preclinical studies have highlighted the potential therapeutic gains that could be achieved by adding EGFR inhibitors to radiation, the best validation of this combination has been from the results of clinical trials in head and neck cancer. A phase III clinical trial demonstrated that, in a cohort of 424 patients with locoregionally advanced squamous cell carcinoma of the head and neck, the addition of cetuximab nearly doubled the median survival of patients (compared to radiotherapy alone), from 28 to 54 months. This study represented the first major success achieved by the addition of an EGFR antagonist to radiotherapy. This improvement was achieved without enhanced toxicity. Notably, the rates of pharyngitis and weight loss were identical in the two arms.

### 1.3 Predicting response to combination cetuximab-radiation

While we hope that we can simply substitute cetuximab for cisplatin-based chemotherapy and achieve the same rate of local control as with chemoradiotherapy without the increased toxicity of chemotherapy, we must also entertain the possibility that only a fraction of these patients will be able to achieve tumor control using this strategy. Therefore, it would be very valuable to be able to predict in advance those patients who will be able to achieve local control with cetuximab and radiation therapy. However, previous efforts to predict the response to EGFR inhibition using the pre-therapy EGFR expression levels have failed. For instance, responses to cetuximab in patients with metastatic colorectal cancer occur in the absence of EGFR staining by immunohistochemistry. Furthermore, the strength of EGFR staining using immunohistochemistry does not predict response to EGFR inhibitors combined with chemotherapy. Previous efforts to predict response in patients with head and neck cancer based on pretreatment EGFR levels have also failed. (Lung cancer may be an exception in this case as mutation of the EGFR may correlate with response, but these mutations are rare in head and neck cancer.) One other recent discovery on the biomarkers of response suggests that patients whose tumors do not have K-ras mutations have a significantly higher disease control rate than patients with K-ras mutations when treated with cetuximab in colorectal cancers. However, K-ras mutation in head and neck cancers is rare, therefore this finding will not be useful for these patients.

Although the focus for developing a predictive assay has been on assessing pretreatment paraffin embedded specimens, it seems possible that a predictive assay may require determining the response to treatment (i.e. a pharmacodynamic endpoint). As has been noted by Mendelsohn and Balsega, successful application of EGFR targeted therapy may require not only the presence of activated EGFR, but also that the cancer depends on this pathway for cell survival. This dependence (“addiction”) might be best determined not simply by assessing pretreatment specimens, but by comparing pre- and post-treatment specimens to determine if the inhibitor has actually inhibited both EGFR phosphorylation and downstream signaling. Indeed, a substantial literature has elucidated these EGFR signaling pathways, which offers candidate molecules. Our preclinical data and the literature

suggest that changes in total EGFR, pEGFR, pSTAT3, and Bcl-XL, EGFR copy number, EGFRvIII status, and NFκB may predict response to cetuximab-radiation. Additionally, we postulate that EGFR variant 3 (EGFRvIII) expression may predict response to cetuximab, since tumors that express primarily this variant are less likely to respond to cetuximab blockade than tumors that express the full length receptor. The vIII form is reported to be intrinsically active and thus blocking ligand binding with the antibody should not be effective. Sok et al. reported that 42% of head and neck tumors in their series expressed EGFRvIII. We will assess vIII expression using RT-PCR with RNA isolated from the research biopsy.

- 1.3.1 In addition to the known downstream effectors of EGFR signaling, it is likely that there are additional downstream targets whose status could add to the known predictive markers described above. Proteomic techniques permit one to assess thousands of potential proteins as possible markers. As much of the key signaling is mediated by phosphorylations and dephosphorylations rather than changes in total protein levels, investigators have focused on the phosphoproteome as a likely source of new candidates 41, 42. Several groups have used these approaches to assess EGF stimulation 43, which has confirmed known pathways and elucidated new targets 44. We are unaware of previous efforts to apply this powerful technology toward the discovery of novel predictors of the effectiveness of combined radiation-cetuximab. We are likewise unaware of studies that have tested the clinical response of EGFR variant three expressing head and neck tumors treated with cetuximab. We postulate that tumors expressing only wild type EGFR will be more responsive than those that express variant III.

## 2.0 Objectives

### 2.1 Primary

- 2.1.1 Determine changes in tumor EGFR, pEGFR, downstream signaling, and novel phosphoproteins following a loading dose of cetuximab in patients who are poor candidates for chemoradiation (age  $\geq 70$  years or with significant co-morbidities) and are therefore treated with cetuximab and radiation.
- 2.1.2 Characterize clinical outcomes, including local recurrence, progression-free survival and overall survival in these patients, and correlate these clinical outcomes with the changes in tumor EGFR, pEGFR, downstream signaling, and novel phosphoproteins.
- 2.1.3 Describe the toxicity, in particular mucositis/dysphagia, of this regimen.

### 2.2 Secondary

- 2.2.1 Conduct normal mucosa EGFR assessment for comparison with tumor sample.
- 2.2.2 Correlate HPV presence and titer with p53 status and clinical outcome.

### **3.0 Inclusion Criteria**

- 3.1** Patients must have pathologically-confirmed, previously untreated, clinically accessible (without general anesthesia) locally advanced squamous cell carcinoma of the larynx, hypopharynx, oropharynx, oral cavity or nonresectable head and neck squamous cell carcinomas of the skin.
- 3.2** Patients will be limited to:
  - $\geq 70$  years of age, **OR**
  - with co-morbidities that preclude treatment with standard platinum-based chemotherapy, as determined by the treating physician, **OR**
  - $KPS \leq 80$ , **OR**
  - Creatinine clearance  $< 30$  cc/min
- 3.3** Laboratory criteria:
  - 3.3.1**  $WBC \geq 3500$ /ul, granulocyte  $\geq 1500$ /ul
  - 3.3.2** Platelet count  $\geq 100,000$ /ul
  - 3.3.3** Total Bilirubin  $\leq 1.5$  X ULN
  - 3.3.4** AST and ALT  $\leq 2.5$  X ULN
- 3.4** Patients must give documented informed consent to participate in this study.

[figure not shown]
### **4.0 Exclusion Criteria**

- 4.1** Prior head and neck malignancy, or history of other prior non-head and neck malignancy within the past 3 years (excluding skin cancer and early stage treated prostate cancer).
- 4.2** Prior head and neck radiation or chemotherapy.
- 4.3** Documented evidence of distant metastases.
- 4.4** Patients with nasopharyngeal carcinoma.
- 4.5** Any medical or psychiatric illness, which, in the opinion of the principal investigator, would compromise the patient's ability to tolerate this treatment.
- 4.6** Patients with psychiatric/social situations that would limit compliance with study requirements are not eligible.
- 4.7** Patients with prior anti-epidermal growth-factor receptor antibody therapy (antibody or small molecule).
- 4.8** Patients residing in prison.

### **5.0 Pre-treatment**

- 5.1** Complete history and physical examination, examination by Otolaryngology, Radiation Oncology, and Medical Oncology, complete documentation of extent of primary tumor and regional disease.
- 5.2** Satisfactory biopsy of the primary tumor confirming pathologic diagnosis.
- 5.3** Complete dental evaluation (at the discretion of physician).
- 5.4** Completion of laboratory studies: Comprehensive panel, including Magnesium and CBCP with differential.
- 5.5** Diagnostic CT scan or MRI of the head and neck.
- 5.6** Initial staging CT-PET scan (at the discretion of physician).
- 5.7** Baseline toxicity evaluation.

## 6.0 Schema

## 7.0 Study Design

### 7.1 Overview

Patients will receive a single dose of cetuximab 400 mg/m^2 (Day 0). On day 7 (+/- 1 day), a repeat biopsy will be performed. Within approximately 4 days, definitive radiation will begin (70 Gy in 35 fractions to the gross tumor, 50-60 Gy to subclinical target volumes) concurrent with weekly cetuximab 250 mg/m^2. Twelve to 14 weeks following the completion of cetuximab-radiation, patients will undergo standard restaging and treatment, including CT-PET, repeat laryngoscopy and tumor site biopsies. Patients with evidence of persistent tumor may undergo surgical salvage and/or neck dissection.

### 7.2 Research Component (Treatment with cetuximab and associated biopsies)

All patients will sign an informed consent for clinical and research biopsies. All biopsies will be performed by an otolaryngologist or oral surgeon who is a co-investigator of the study. The proposed tissue accrual should be adequate for all of the proposed studies.

- 7.2.1 Research Biopsy #1: Patients will be consented and enrolled in this study prior to this biopsy. The biopsy will be performed no more than 4 weeks prior to the loading dose of cetuximab. It will be performed under local anesthesia (in the event a patient requires further clinical staging or confirmation of diagnosis under general anesthesia, the research biopsy may be performed at that time.) This pre-treatment biopsy will be performed for research purposes if a suitable clinical biopsy specimen is not available. A clinical specimen will be suitable if the biopsy was performed within 4 weeks of the loading dose of Cetuximab.
- 7.2.2 Research Biopsy #2: This will be done 7 days (+/- 1 day) after the cetuximab loading dose (Day 0).
- 7.2.3 Normal Oral Mucosa Sampling: Baseline EGFR of the normal oral mucosa will be obtained by buccal swab or normal mucosa biopsy. If using buccal swabs, at least 3 normal oral mucosa buccal swab

samples will be acquired. This sampling will occur at both Research Biopsy #1 and Research Biopsy #2.

**7.3 Cetuximab/Radiation Schedule:** Cetuximab will be delivered as standard of care per the package insert.

- 7.3.1 Day 0: Patients will receive a single dose of cetuximab 400 mg/m^2.
- 7.3.2 Day 7 (+/- 1 day): Biopsy #2 will be obtained
- 7.3.3 Following the biopsy, within approximately 4 days, daily radiation therapy with weekly cetuximab will be initiated.
- 7.3.4 Patients will receive weekly cetuximab 250 mg/m^2. On days of radiation therapy and cetuximab administration, cetuximab will be given prior to radiation therapy.

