#### 13.0 EGFR analysis (General Laboratory Guidelines)

The primary goal of this analysis is to determine whether cetuximab given at the clinically recommended dose, will inhibit EGFR phosphorylation and down-stream signaling effects within the tumor as well as the normal mucosa following therapy. In addition, the activation of EGFR and various down-stream signaling markers will be measured using immunoblotting as well as immunohistochemical analysis in both normal and tumor samples at baseline and post-treatment.

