#### 13.4

##### Pre-Cetuximab tumor

The initial pre-treatment punch-biopsy specimen (about 3x3x3 mm) of the tumor will be collected in the presence of a laboratory personnel and will be immediately frozen in dry-ice ethanol bath in Tissue-Tek O.C.T Compound (Sakura Finetek, Torrance, CA) to ensure the integrity of tissue and phosphoproteins for both immunoblotting and immunohistological analysis of samples. We will be able to take 3 cores for TMA construction from a single 3x3x3 mm biopsy and will expect to have enough material to get about 30-50 4-5 micrometers thick sections for immunohistochemical analysis.

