#### 13.5

##### Method of Assessment of EGFR Expression in Tumor After Cetuximab

##### Loading Dose

At the time of the second biopsy, four core biopsies from different areas of the tumor as well as swab of the normal appearing mucosa will be obtained. Four core biopsies will be processed with one core used in high-throughput immunoblot analysis, one core will be fixed in formalin to be embedded in paraffin, one core will be frozen and fixed in Tissue-Tek OCT for immunofluorescence analysis and one core will be used for RNA and DNA isolation using Trizol. EGFR phosphorylation analysis using immunoblotting and immunohistochemistry will be performed in the surgical specimen and immunofluorescence analysis will also be performed if sufficient tissue is available using standard methods. Interpretations of the staining will be performed according to the standard guidelines. The EGFR and critical associated down-stream signaling pathways will be analyzed post- induction therapy, including p-EGFR and total EGFR, p-ERK1/2, p-AKT, p27, Ki-67, and p-STAT3, and other markers that we may discover in our preclinical studies. EGFRvIII expression and p53 mutation analysis will be assessed on cDNA obtained from total RNA converted with RT-PCR. Genomic DNA from the tumor biopsy will be used to test for HPV presence and type as carried out by PCR-mass spect using the AttoSense assay at SensiGen, LLC.

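### Baseline and Day 7 tumor tissue are not tied to one preservation procedure, so handling can be confounded with the marker change tested in Primary Objective 1

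*Combined protocol and SAP*

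**What the plan says.** **Which specimen is the baseline.** Section 7.2.1: "This pre-treatment biopsy will be performed for research purposes if a suitable clinical biopsy specimen is not available". Suitability is then defined: "A clinical specimen will be suitable if the biopsy was performed within 4 weeks of the loading dose of Cetuximab". The same item says that patients are consented and enrolled before this biopsy, and 7.2 says that co-investigators perform all biopsies. Neither statement concerns preservation.

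**What is measured.** Section 13.0 has EGFR activation and downstream markers "measured using immunoblotting as well as immunohistochemical analysis in both normal and tumor samples at baseline and post-treatment".

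**Baseline handling, 13.4.** The punch is "immediately frozen in dry-ice ethanol bath in Tissue-Tek O.C.T Compound", with laboratory personnel present, "to ensure the integrity of tissue and phosphoproteins", for both immunoblotting and immunohistology. It is also a source for the tissue microarray: "We will be able to take 3 cores for TMA construction from a single 3x3x3 mm biopsy".

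**Day 7 handling, 13.5.** "Four core biopsies will be processed with one core used in high-throughput immunoblot analysis, one core will be fixed in formalin" and embedded in paraffin; "one core will be frozen and fixed in Tissue-Tek OCT for immunofluorescence analysis"; the fourth core goes to nucleic acid isolation.

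**Appendix B.** One description covers both biopsies: ice-cold saline with protease and phosphatase inhibitors, then division into three parts, with the array built from the formalin-fixed part. The immunoblotting paragraph instead has samples stored immediately in Allprotect. The array paragraph plans one array of about 200 cores, from tissue before and after treatment, with at least three replicate cores per subregion.

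**Analysis.** Section 21.3.1 tests with a one-sample t-test whether mean change, absolute or as a percentage of baseline, is zero. Section 21.3.2 enters the marker changes in logistic and Cox models. Section 21.2 asks for 50 patients who undergo both biopsies; tissue preservation is not part of evaluability.

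**The concern.** The trial has no untreated biopsy pair. If baseline tissue is preserved in one way and Day 7 tissue in another, the average effect of that difference adds directly to the mean change, and the t-test cannot separate it from cetuximab. Signal lost only at baseline would hide a true fall in a phosphoprotein; signal lost only at Day 7 would look like one. Section 13.4 itself treats handling as important to phosphoprotein integrity.

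This has to be settled before tissue is taken, because preservation cannot be undone at analysis. Since evaluability depends on undergoing the two biopsies, the number of like-handled pairs could also be below 50 without anyone having to report it.

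**Working it through.** **1. Handling texts side by side**

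| Source | Applies to | Immediate handling | Array tissue |
|---|---|---|---|
| 7.2.1 | clinical baseline specimen | not stated; timing rule only | not stated |
| 13.4 | baseline | one punch frozen in O.C.T. | three cores from the frozen punch |
| 13.5 | Day 7 | four cores, four routes; preservation of the immunoblot core not stated | not stated |
| Appendix B, collection | both | ice-cold saline with inhibitors, three parts | formalin-fixed part |
| Appendix B, immunoblotting | both (no distinction made) | Allprotect | not stated |

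Under 13.4 and 13.5, only the Day 7 O.C.T. core has a stated like-handled baseline partner. The formalin core has none in 13.4. For the immunoblot core the text is silent, which is not the same as a stated difference. Each Appendix B description is symmetrical between time points, but a specimen cannot go immediately into both media, and neither is the freezing of 13.4. No passage ranks the texts.

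**2. Where a shift would enter**

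Let the observed absolute change be D = true change + h, where h is the handling difference.
- Test of mean change: the expected mean of D is the true mean + mean(h), so the test is biased whenever mean(h) is not zero.
- Outcome models: if h is the same constant for every patient, adding it to D leaves the Cox or logistic slope unchanged. If h varies between patients (some clinical baselines, some frozen ones), it adds noise, and bias if it is related to prognosis. For percent change, an offset in the baseline also alters the denominator, so the invariance does not carry over.

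**3. Size**

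The documents give no signal-loss figure and no expected share of clinical baselines, so mean(h) is unknown. Purely as illustration, take no drug effect, 50 pairs, a two-sided 0.05 t-test and noncentrality d x sqrt(50). An assumed mean(h) of 0.1, 0.2, 0.3 or 0.4 SD of the change gives a significant result in 11%, 28%, 55% or 79% of trials. These shifts are not estimates.

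**4. Array count (planned figure: about 200)**

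Inputs: 50 evaluable patients and two biopsies each (21.2); at least three cores per subregion (Appendix B).
- One time point: 50 x 1 x 3 = 150.
- Two time points: 50 x 2 x 3 = 300; with two subregions per sample, 600.
- 200 is reproduced only by departing from three cores for every pair: 50 x 2 x 2 = 200, or 200 / (2 x 3) = 33.3, that is 33 complete pairs.

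**5. Precision if fewer pairs are like-handled**

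Mean change detectable at 80% power (two-sided 0.05, one-sample t):

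| Pairs | Detectable change (SD) |
|---|---|
| 50 | 0.40 |
| 40 | 0.45 |
| 33 | 0.50 |
| 25 | 0.58 |

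For the marker-PFS model, I simulated the design in 21.4: exponential PFS with median 22 months, uniform accrual over 36 months, analysis six months later, marker difference of 1.1 SD. With 50 patients, power is about 84% if the SD is within group and 93 to 94% if it is the total SD, which agrees with the plan's statement of at least 80%. On the within-group reading it falls to about 75% with 40 patients, 65% with 33 and 52% with 25.

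**The case against.** The best defence is that Appendix B is written for both biopsies, so the intent was common handling and choosing between its two descriptions creates no baseline/Day 7 bias. That stands. A reader might infer that the plan prescribes different preservation at the two time points; the documents do not support this, because asymmetry follows only if 13.4 and 13.5 govern or a differently preserved clinical specimen is used. What remains is that nothing says Appendix B governs and that it contradicts itself.

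A second defence is that 7.2.1 has consent and enrolment come first and that 13.4 does not exempt specimens taken for clinical purposes, so a clinical biopsy may fall under the freezing rule. That reading is open. So is the other one: the suitability sentence is worded in the past tense and admits an existing specimen. One should not infer that archived diagnostic tissue will be used, only that the text does not prevent it.

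Third, the sample size rests on Primary Objective 2, and a uniform offset does not move the slope for an absolute change. This stands, and it rules out the inference that the marker-outcome analysis is invalid as a whole.

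Fourth, 13.5 names Trizol and Appendix B names Qiagen kits for nucleic acid. A reader might add this to the confounding argument. It does not belong there: that material serves EGFRvIII, p53 and HPV assays, not the phosphoprotein change test. It is only a wording mismatch to tidy.

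Finally, Appendix B nowhere says that all 50 pairs are arrayed, so 300 is a derived figure.

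**Conclusion.** The point holds as a conflict between procedures that bears on a primary analysis. Section 7.2.1 sets a timing rule without a preservation condition, 13.4 and 13.5 do not match, Appendix B gives two incompatible common procedures, and no text governs. Followed as written, these can confound preservation with the test that mean change is zero. For Primary Objective 2 the risk is confined to handling that differs between patients, and to percent change. The size is unknown; a reader should not take the illustrative rejection rates as an estimate, nor conclude that the results will be biased.

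The array count is minor and separate. The planned 200 is one third below the implied 300, assuming that all 50 pairs are arrayed with one subregion each. It affects array-scored markers only, and no pair need be lost if two cores per biopsy or a second block is used. The sponsor should correct both; the handling conflict carries the weight.

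**What to change.** 1. Reconcile 13.4, 13.5 and Appendix B into one procedure per assay that applies to both time points, including the source of array tissue, and state which section governs.
2. In 7.2.1 keep the 4-week rule and add that a clinical specimen is suitable for an assay only if it was preserved in the same way as Biopsy #2 for that assay.
3. In 21.3.1 and 21.3.2 record the handling of each pair, report the number of like-handled pairs beside the 50, and repeat the phosphoprotein change analyses in those pairs as a sensitivity analysis. Evaluability and replacement in 21.2 can stay as they are.
4. Restate the array as at least 300 cores (each pair on the same block if two are used), as two cores per biopsy, or as covering about 33 pairs.

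**Cost.** Wording in five places, a handling field in the data, and possibly a second array block. Because 7.2.1 already provides for a research biopsy when no suitable clinical specimen exists, item 2 may lead to more of them; the text should say whether it does, or whether the patient is simply absent from the like-handled set for that assay. The sensitivity analysis will be less precise: 10 lost pairs raise the detectable mean change from 0.40 to 0.45 SD and 25 lost pairs raise it to 0.58 SD, with lower power for the marker-PFS model in that subset. The analysis of all 50 is unaffected.
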